**Parameters with NCI-CTC grades available:**

The laboratory toxicities will be tabulated using descriptive statistics (number of subjects and percentages) during the on-treatment period:

- The summary of laboratory parameters by CTCAE grade table will include number and percentage of subjects with Grade 1, 2, 3, 4, 3/4, and any grade, laboratory abnormalities during the on-treatment period.

- The shift table will summarize baseline CTCAE grade versus the worst on-treatment CTCAE grade. The highest CTCAE grade during the on-treatment period is considered as the worst grade for the summary.

The above analyses apply to hematology and chemistry evaluations which can be graded per CTCAE, i.e.:

- Hematology:

Hemoglobin (HB), Leukocytes (white blood cell decreased), Lymphocytes (lymphocyte count increased/decreased), Neutrophils / Absolute Neutrophils Count (ANC) (neutrophil count decreased), Platelet Count (PLT) (platelet count decreased).

- Serum Chemistry:

Albumin (hypoalbuminemia), Alkaline Phosphatase (ALP) (alkaline phosphatase increased), Alanine Aminotransferase (ALT) (ALT increased), Amylase (serum amylase increased), Aspartate Aminotransferase (AST) (AST increased), Total Bilirubin (blood bilirubin increased), Cholesterol (cholesterol high), Creatinine (creatinine increased), Creatine Kinase (CPK increased), Potassium (hypokalemia/hyperkalemia), Sodium (hyponatremia/hypermagnesemia), Magnesium (hypomagnesemia/hypermagnesemia), Calcium (hypocalcemia/hypercalcemia), Glucose (hypoglycemia/ hyperglycemia), Gamma Glutamyl Transferase (GGT) (GGT increased), Lipase (lipase increased), Phosphates (hypophosphatemia), Triglycerides (hypertriglyceridemia).

**Parameters with NCI-CTC grades not available:**

Hematology and chemistry tests which cannot be graded per CTCAE criteria will be summarized as frequency (number and percentage) of subjects with:

- shifts from baseline normal to at least one result above normal during on-treatment period
- shifts from baseline normal to at least one result below normal during on-treatment period

In this study, these apply to the following laboratory tests:

- Hematology:

Basophils (absolute and percent), Eosinophils (absolute and percent), Monocytes (absolute and percent), Neutrophils (absolute and percent), Hematocrit, Red Blood Cell (RBC), Reticulocytes, Mean Corpuscular Hemoglobin (MCH), Mean Corpuscular Volume (MCV), Mean Corpuscular Hemoglobin Concentration (MCHC).

- Serum Chemistry:

Chloride, C-Reactive Protein, Lactate Dehydrogenase (LDH), Total Protein, Total Urea, Uric Acid.

### 16.3.2 Other Laboratory Parameters

All other parameters collected on the eCRF will be listed in dedicated listings presenting all corresponding collected information on the eCRF.

- Hemostaseology: activated partial thromboplastin time (aPTT), prothrombin time (PT), and International Normalized Ratio (INR).
- Urinalysis: all urinalysis parameters
- Other parameters: hormone and immunology parameters
- Pregnancy test

Listings of laboratory results will be provided for all laboratory parameters. These listings will be sorted by parameters and assessment dates or visits for each subject; laboratory values that are outside the normal range will be flagged along and corresponding normal ranges will be provided in addition to NCI-CTCAE grade.

In addition, listings of abnormal values will be provided for chemistry and hematology parameters. If there is at least one abnormal result for any parameter, all the data for that parameter will be included in the listing. For all tests not mentioned above but present in the clinical data, a listing of subjects with at least one result for the relevant test will be provided.

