7.4.3 Clinical Laboratory Assessments

All laboratory samples that are detailed in the Schedule of Assessments (see Table 1 to Table 7) must be collected, and sent to the central laboratory for analysis. Serum β -hCG pregnancy tests may be analyzed locally.

Sample for complete blood count and core chemistry must be available and reviewed prior to dose administration. Results of all central laboratory testing will be transferred to the clinical database.

Urinalysis and urine pregnancy testing will be done locally.

Local laboratory samples may be drawn and if collected are required to be recorded in the eCRFs.

In the case of liver function test (LFT) elevations (AST, ALT and/or total bilirubin) requiring additional lab draws (according to guidelines set forth in Table 11 Management of irAEs), an unscheduled lab draw should be sent to the central laboratory for analysis.

Cardiac troponin levels will be collected from Re-baseline up to 12 weeks in the Maintenance Phase. Cardiac troponin levels will be evaluated centrally. Local laboratories may be used at the discretion of the Investigator as clinically needed for safety management/treatment decision of the subject. Measurement of cTnT is preferred, however cTnI may be substituted where cTnT is not available at the local laboratory. The same subunit (cTnT or cTnI) measured at the Re-baseline visit should be measured consistently throughout the study in each patient. At the Re-baseline visit, clinically significant positive results should be further assessed as per local SOC to rule-out concurrent cardiac conditions which would make the patient ineligible for the study as per exclusion criteria. During the study, clinically significant new elevations suggestive of myocarditis should be assessed as per Table 11. Additional tests should also be performed when clinically indicated.

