Observed and change from baseline values during the Maintenance Phase will be summarized by visit, test, and treatment arm for chemistry and hematology laboratory results. Laboratory results will be classified by grade according to NCI-CTCAE. The worst on-treatment grades during the Maintenance Phase for chemistry and hematology laboratory results by treatment arm will be summarized. Shifts in toxicity grading from baseline to highest grade during the Maintenance Phase by treatment arm will be displayed. Results during the Maintenance Phase for laboratory tests that are not part of NCI-CTCAE will be presented categorically (eg, below, within, or above normal limits) by treatment arm. Only subjects with post-baseline laboratory values will be included in these analyses. Urinalysis results will be listed only. Further details of analyses for the laboratory parameters will be provided in the trial SAP.

ECOG Performance Status

Shifts from Re-baseline (end of Induction Phase) in ECOG PS score will be presented at planned visits during the Maintenance Phase, the Discontinuation Visit, and End-of-Treatment Visit by number and percentage for each treatment arm. Shifts from Re-baseline to highest on-treatment ECOG PS score will be summarized in a similar fashion.

Physical Examinations

Clinically significant, abnormal findings from physical examinations before ICF signature are to be reported as pre-existing medical conditions and will be included in summaries of medical history. On the other hand, clinically significant, abnormal findings from physical examinations after ICF signature are to be reported as AEs and will be included in summaries of AEs.

Vital Signs

Maximum on-treatment increase and maximum on-treatment decrease from baseline values during the Maintenance Phase will be summarized by parameter (eg, body temperature, respiratory rate, heart rate, and blood pressure) using descriptive statistics by treatment arm. A similar summary will be provided for the Induction Phase by total number of subjects.

12-Lead ECGs

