## 8 Changes to the Planned Analyses in the Clinical Trial Protocol

The statistical methods specified in this SAP are in accordance with protocol version 7.0 (dated 17 July 2019), with the following exception:

- Subjects randomized to the chemotherapy arm, who are designated to receive BSC-only, will have the date of their Week 1 Day 1 assessment considered as “treatment start date”. Consequently, this date will be used for determining baseline for Safety endpoints. This differs from the protocol, which specifies that the date of randomization will be used for both. Use of the Week 1 Day 1 assessment date more closely mirrors how subjects randomized to active treatment are handled.

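### SAP 16.3 gives TSH, free T4 and cardiac troponin no by-arm summary; for TSH and free T4 this is an undeclared departure from the most natural reading of Protocol 8.5.5

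*SAP*

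**What the plan says.** **Protocol 8.5.5, Laboratory Values.** For the Maintenance Phase, "laboratory tests that are not part of NCI-CTCAE will be presented categorically (eg, below, within, or above normal limits) by treatment arm". One exception follows: "Urinalysis results will be listed only". The section's opening is narrower and describes the laboratory review as serum chemistry, hematology and urinalysis.

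**Protocol 7.4.3 and Table 12.** TSH and free T4 are in the table of clinical laboratory assessments, in a row separate from the hormone row, which names only FSH. For troponin, "Cardiac troponin levels will be collected from Re-baseline up to 12 weeks in the Maintenance Phase", with central evaluation. Tables 3 to 6 schedule all three analytes for avelumab, both chemotherapy regimens and BSC-only.

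**SAP 16.3.1.** One closed list names the tests graded by CTCAE. A second names the ungraded hematology and chemistry tests that get a table of shifts from normal. The ungraded chemistry entries are chloride, C-reactive protein, LDH, total protein, urea and uric acid.

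**SAP 16.3.2.** What remains goes to listings: "All other parameters collected on the eCRF will be listed in dedicated listings presenting all corresponding collected information on the eCRF". The items include "Other parameters: hormone and immunology parameters", and a closing rule covers anything unnamed: "For all tests not mentioned above but present in the clinical data, a listing of subjects with at least one result" for the relevant test.

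**SAP 8.** "The statistical methods specified in this SAP are in accordance with protocol version 7.0 (dated 17 July 2019), with the following exception". The single exception concerns the treatment start date for BSC-only subjects.

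**The concern.** Protocol 3.3.1 names thyroid disorders and myocarditis among the important risks of avelumab. TSH, free T4 and troponin are scheduled measurements bearing on those risks, taken in both arms on a fixed calendar whether or not anyone reports an event. In an open-label trial that makes them a useful check on the adverse event comparison.

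The adverse event route is filtered. Under Protocol 7.4.1.1 an abnormal result is reported as an AE only if it comes with signs or symptoms, leads to discontinuation, or is otherwise judged medically important. The medically assessed irAE tables show counts for avelumab alone (SAP 16.2.3) and require that corticosteroids, immunosuppressants or hormonal therapy were given (SAP Appendix IV), so an untreated biochemical thyroid abnormality cannot qualify. At stake is a planned descriptive comparison of how often these results become abnormal in each arm.

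**Working it through.** There is no figure in the plan to reproduce. The check is a comparison of text, plus a count of scheduled samples.

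**1. Reach of the protocol sentence.** In the same paragraph of Protocol 8.5.5, the by-visit and worst-grade summaries are expressly limited to chemistry and hematology. The sentence on tests outside CTCAE has no such limit. Its lone listing-only exception is urinalysis, so hormones are not exempted.

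**2. Where each analyte lands in the SAP.**

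| Analyte | Graded list, 16.3.1 | Shift list, 16.3.1 | Destination |
|---|---|---|---|
| TSH | no | no | listing |
| Free T4 | no | no | listing |
| Troponin | no | no | listing, through the rule for unnamed tests |

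By-arm laboratory summaries: 0 of 3 analytes. Placing TSH and free T4 under hormone parameters is an inference. If that phrase meant only FSH, they would fall to the rule for unnamed tests, with the same result.

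**3. Does another SAP sentence rescue them?** SAP 16.3.1 repeats the protocol's idea that results outside CTCAE are shown against normal limits. It stands under the hematology and chemistry heading and is carried out through the closed shift list. SAP Table 8 has a row for shifts relative to normal range but names no tests.

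**4. Scheduled samples (Protocol Tables 3 to 6).**

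- TSH and free T4: Re-baseline, Weeks 7 and 13, then every 6 weeks, end of treatment and the 30-day visit, identical in all four tables. A subject on treatment to Week 25 has post-baseline pairs at Weeks 7, 13, 13 + 6 = 19 and 19 + 6 = 25, which is 4.
- Troponin on avelumab or 5-FU: Weeks 1, 3, 5, 7, 9, 11 and 13, which is 7 visits.
- Troponin on capecitabine or BSC: Weeks 1, 4, 7, 10 and 13, which is 5 visits.
- Under SAP 10 a planned Week 1 Day 1 assessment without a recorded time is taken as pre-dose, and for BSC-only the safety baseline runs through that visit. Week 1 is therefore normally baseline. Post-baseline samples are 7 − 1 = 6 and 5 − 1 = 4, a ratio of 6/4 = 1.5.
- Post-baseline weeks common to all four schedules: 7 and 13.

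A worst-value troponin table would thus give some control subjects fewer chances of an abnormal result. TSH and free T4 have no such imbalance in visit schedule.

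**The case against.** **The protocol may never have meant these tests.** The opening of 8.5.5 names only chemistry, hematology and urinalysis. Urinalysis is the third of those, so the exception also fits the narrow reading. This makes the scope arguable, but it does not put a limit into the later sentence.

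**The SAP may add detail or change the plan.** Protocol 8.5.5 leaves laboratory details to the SAP, and Protocol 8.5.1 lets the SAP modify planned analyses, with an amendment only for major changes. That is fair, but SAP 8 claims accordance with one exception and this is not it.

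**Other outputs cover these risks.** A reader might infer that the arms cannot be compared on thyroid or cardiac toxicity at all. The documents do not support that. TEAEs are tabulated by treatment group (SAP 16.1). Potential irAEs, identified by preferred term alone, are counted in both arms (SAP 16.2.3), so the treatment criterion in Appendix IV does not restrict them. Creatine kinase is graded, ECGs are summarised by group, and listings flag out-of-range results with normal ranges. What stands is narrower: the event tables count reported events, and none of these outputs gives a by-arm rate of abnormal TSH, free T4 or troponin.

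**Reporting is not purely discretionary.** Of the three AE criteria in Protocol 7.4.1.1, only the third expressly rests on investigator judgement, and Protocol 7.4.3 sends clinically significant new troponin elevations suggestive of myocarditis to Table 11. This weakens any claim that event counts merely reflect opinion.

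**Troponin may be gradable.** A reader might infer that the protocol sentence on tests outside CTCAE is breached for troponin. The documents never state its CTCAE status, so the conflict with that sentence is shown only for TSH and free T4. For troponin the finding is simply that neither SAP list includes it.

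**Conclusion.** The point holds. Followed as written, the SAP produces no by-arm laboratory summary for TSH, free T4 or troponin. For TSH and free T4 this departs, without declaration, from the protocol sentence read on its own terms. For troponin it is a gap under either CTCAE status.

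The size is modest. Safety outputs are descriptive, the data remain listed, and neither the primary analysis nor type I error control is affected. The omission touches every subject in the Safety-Maintenance set, drawn from the 499 randomised, who has these scheduled results.

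The conclusion rests on two assumptions: that the laboratory sentence in Protocol 8.5.5 is not silently limited by the section's opening, and that no redacted SAP text supplies the missing summary. The documents make thyroid and cardiac immune toxicity important risks; they do not rank these tests among possible markers, and the point does not need them to.

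**What to change.** In SAP 16.3.1:

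- Add TSH and free T4 to the by-arm table of subjects moving from a normal baseline to a result above or below normal on treatment, and take them out of the listing-only group in 16.3.2 (the individual listings can stay).
- Add troponin by arm as movement from a normal baseline to above normal, with cTnT and cTnI kept separate because Protocol 7.4.3 allows either. Include rows at Weeks 7 and 13 so that the 6 against 4 sampling difference does not drive the comparison.

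If the sponsor instead intends listings only, SAP 8 should say so and give the reason. A cross-tabulation of TSH direction against free T4 direction would help interpretation but is optional; no document plans it.

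The cost is a short SAP edit and one or two extra descriptive tables from data already collected. No visit, sample or clinical procedure changes.

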### 16.4 Vital Signs

*Analysis set: Safety-Maintenance Analysis Set*

Vital sign summaries will include all vital sign assessments from the Maintenance Phase on-treatment period. All vital sign assessments will be listed, and those collected outside the on-treatment period will be flagged in the listing.

All vital sign parameters will be summarized using descriptive statistics (mean, SD, median, Q1, Q3, minimum, and maximum) of actual values and changes from baseline for each visit over time. End of treatment and Safety follow-up visits will be summarized separately. The changes computed will be the differences from baseline.

For each subject the maximum on-treatment increase/decrease from baseline will be calculated and categorized by vital sign measurement (see [Table 9](#)). Missing values will define a separate category. A summary of maximum shift from baseline by category will be provided by treatment arm. A summary of maximum change from baseline per subject will also be provided.

**Table 9 Categories of Change from Baseline for Vital Sign Parameters**

Parameters	Categories of Change from Baseline
Body temperature increase	< 1°C, 1-<2°C, 2-<3°C, ≥ 3 °C
Weight increase	<10%, ≥ 10%
Weight decrease	<10%, ≥ 10%
Heart rate increase from baseline <100 bpm; ≥ 100 bpm	≤20 bpm, >20 – 40 bpm, >40 bpm
Heart rate decrease from baseline <100 bpm; ≥ 100 bpm	≤20 bpm, >20 – 40 bpm, >40 bpm
SBP increase from baseline <140 mmHg; ≥ 140 mmHg	≤20 mmHg, >20 – 40 mmHg, >40 mmHg
SBP decrease from baseline <140 mmHg; ≥ 140 mmHg,	≤20 mmHg, >20 – 40 mmHg, >40 mmHg
DBP increase from baseline <90 mmHg; ≥ 90 mmHg	≤20 mmHg, >20 – 40 mmHg, >40 mmHg
DBP decrease from baseline <90 mmHg; ≥ 90 mmHg,	≤20 mmHg, >20 – 40 mmHg, >40 mmHg
Respiration rate increase from baseline <20 bpm; ≥ 20 bpm	≤5 breaths/min, >5 – 10 breaths/min, >10 breaths/min
Respiration rate decrease from baseline <20 bpm; ≥ 20 bpm	≤5 breaths/min, >5 – 10 breaths/min, >10 breaths/min

bpm = beats per minute for heart rate and breaths per minute for respiration rate;  
DBP=diastolic blood pressure; SBP=systolic blood pressure

## 16.5 Other Safety or Tolerability Evaluations

*Analysis sets: Safety-Induction Analysis Set, Safety-Maintenance Analysis Set*

### 16.5.1 ECG

A 12-lead Electrocardiogram (ECG) assessment will be performed at the Screening, Re-Baseline and at the Discontinuation/End-of-Treatment visits. ECG summaries will include all ECG assessments from the Maintenance Phase on-treatment period. All ECG assessments will be listed, and those collected outside the on-treatment period will be flagged in the listing.

For each of the ECG parameters (heart rate, QTcB, QTcF, QRS interval, PR interval), descriptive statistics at baseline (see Section 10 for definition), at each post-baseline time point and changes from baseline at each post-baseline time point will be summarized by treatment group.

Frequency (number and percentage) of subjects with the worst potentially clinically significant abnormalities (PCSA) for ECG parameters during the on-treatment period will be summarized. Each subject will be counted only once within each category. As ECG assessments are only performed

during Screening, Re-Baseline and at the Discontinuation/End-of-Treatment visit, the denominator to calculate percentages for each PCSA category is the number of subjects with a Discontinuation/End of Treatment visit. The PCSA criteria are provided in Table 10.

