Concomitant procedures	Collected from Screening through End-of-Treatment Visit						
AE and SAE collection	Collected from Informed Consent through End-of-Treatment Visit ^b						X
Samples and Laboratory Assessments							
Hematology and hemostaseology ^g	X	X	X	X	X	X	X
Full serum chemistry ^h	X					X	
Core serum chemistry ^h		X	X	X	X		X
Urinalysis ⁱ	X					X	X
β-hCG pregnancy test ^j	X	X	X	X	X	X	
HBV and HCV test ^k	X						
T ₄ and TSH	X			X		X	

Dosing						
Premedication [¶]		X	X	X	X	
Chemotherapy administration		X	X	X	X	

AE = adverse event; β -hCG = β -human chorionic gonadotropin; CT = computed tomography; D = day; ECG = electrocardiogram; ECOG PS = Eastern Cooperative Oncology Group Performance Status; EOT = end of treatment; HBV = hepatitis B virus; HCV = hepatitis C virus; ICF = informed consent form; CCI [redacted]; CCI [redacted]; RNA = ribonucleic acid; SAE = serious adverse event; T₄ = free thyroxine; TSH = thyroid-stimulating hormone; W = week.

- a A time window of up to 4 days before or 2 days after the scheduled Day 1 visit (-4 / +2 days) will be permitted for all trial procedures for the Day 1 visit of each cycle. Subjects should also return to the trial site as per local institutional practice for any additional routine assessments during chemotherapy.
- b Subjects who discontinue the Induction Phase due to any reason will have an EOT visit within 7 days of the decision to discontinue chemotherapy. All subjects who do not enter the Maintenance Phase will have a 30-day after last treatment Safety Follow-up visit. Subjects entering the Maintenance Phase will have the Re-baseline visit (Table 3 to Table 6 as applicable). Subjects with an AE ongoing at the EOT visit must be followed up for final outcome until the 30-day Safety Follow-up visit. Subjects with an SAE ongoing at the 30-day Safety Follow-up visit must be monitored and followed up by the Investigator until stabilization or until the outcome is known, unless the subject is documented as “lost to follow-up.”
- c Subjects who complete Cycle 4 will return to clinic for the Re-baseline visit (see Table 3 to Table 6 depending on regimen). The Re-baseline visit is to occur -10 to -1 days before the first administration in the Maintenance Phase.

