## 16 Safety Evaluation

The subsections in this section include specifications for summarizing safety endpoints that are common across clinical trials such as adverse events, laboratory tests and vital signs. All safety related summary tables will be summarized for the on-treatment period of the Induction and/or Maintenance Phase and the analysis sets specified in Table 8. The safety endpoints will be tabulated using descriptive statistics.

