**Table 8 Safety Analyses by Analysis Set and Study Phase**

	Safety – Induction Analysis Set	Safety-Maintenance Analysis Set	
	Induction Phase	Induction Phase	Maintenance Phase
AEs			
Overall Summary by Category	Y	Y	Y
All TEAEs	Y	Y	Y
Related TEAEs	Y	Y	Y
Serious TEAEs	Y	Y	Y
NCI CTC AE Toxicity Grades	Y	Y	Y
AEs Leading to Discontinuation	Y		Y
AEs Leading to Death	Y		Y
irAEs			Y
IRRs			Y
Labs			
Descriptive Statistics		Y	Y
NCI CTCAE Toxicity	Y	Y	Y
Shifts Relative to Normal Range			Y
Vital Signs			
Descriptive Statistics			Y
Change Categories			Y
ECG			
Descriptive Statistics			Y
PCSA Criteria	Y	Y	Y

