**Table 10 PCSA Criteria for ECG Test Results**

Test	PCSA Criteria
Heart Rate	≤ 50 bpm and decrease from baseline ≥ 20 bpm ≥ 120 bpm and increase from baseline ≥ 20 bpm
PR Interval	≥ 220 msec and increase from baseline ≥ 20 msec
QRS Interval	≥ 120 msec
QTcF and QTcB absolute	Interval >450 msec and interval ≤ 480 msec Interval >480 msec and interval ≤ 500 msec Interval >500 msec
QTcF and QTcB change from baseline	Increase from baseline > 30 msec and ≤ 60 msec; Increase from baseline > 60 msec

QTc will be corrected based on Fridericia’s formula for QTcF and Bazett's formula for QTcB ( $QTcF = QT / \sqrt[3]{RR}$  and  $QTcB = QT / \sqrt{RR}$ ) where RR=60/HR. Baseline QTcF and QTcB will be derived from the visit that other ECG parameters are flagged as baseline. If there are multiple assessments at the same visit and time point, the average will be calculated for each parameter and used for the analysis.

[figure not shown]
Subjects with notable ECG interval values and qualitative ECG abnormalities will be listed for each subject and time point and the corresponding notable values and abnormality findings will be included in the listings.

[figure not shown]
Unscheduled ECG measurements will not be used in computing the descriptive statistics for change from baseline at each post-baseline time point. However, they will be used in the analysis of notable ECG changes and the shift table analysis of notable QT parameters.

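### SAP Table 8 calls for Induction Phase ECG PCSA tables, but Section 16.5.1 gives them a scope and a denominator that work only for the Maintenance Phase

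*SAP*

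**What the plan says.** **Which tables are planned.** SAP Section 16 introduces Table 8 with: "All safety related summary tables will be summarized for the on-treatment period of the Induction and/or Maintenance Phase". The ECG row of Table 8 reads "PCSA Criteria Y Y Y". The three columns are Safety-Induction set/Induction Phase, Safety-Maintenance set/Induction Phase and Safety-Maintenance set/Maintenance Phase.

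**Scope.** SAP 16.5.1 states: "ECG summaries will include all ECG assessments from the Maintenance Phase on-treatment period".

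**Numerator.** The same section counts subjects by their worst abnormality: "potentially clinically significant abnormalities (PCSA) for ECG parameters during the on-treatment period will be summarized". Each subject counts once per category.

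**Denominator.** Because ECGs are scheduled only at Screening, Re-baseline and Discontinuation/End of Treatment (EOT), "the denominator to calculate percentages for each PCSA category is the number of subjects with a Discontinuation/End of Treatment visit". There is no split by phase.

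**Unscheduled ECGs.** The text after SAP Table 10 leaves them out of the by-visit descriptive statistics, then adds: "However, they will be used in the analysis of notable ECG changes and the shift table analysis of notable QT parameters".

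**Who has which visit.** Footnote b of Protocol Tables 1 and 2 gives an Induction EOT visit to subjects who discontinue Induction. For the others: "Subjects entering the Maintenance Phase will have the Re-baseline visit (Table 3 to Table 6 as applicable"). Protocol 7.1.3 lists a 12-lead ECG at Re-baseline.

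**Induction on-treatment period.** SAP Section 10 ends it at the earliest of last induction dose plus 30 days, the day before a new anti-cancer drug, and the day before Maintenance treatment starts.

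**The concern.** A PCSA percentage should be the share of subjects with an evaluable on-treatment ECG who crossed the threshold. That requires every subject who can enter the numerator to be in the denominator. In Induction, the subjects who reach randomisation have their on-treatment ECG at a visit that the denominator does not count. Section 16.5.1 and Table 8 also disagree on whether Induction ECGs are summarised at all, so a programmer cannot build two of the three planned tables from the text.

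At stake are the descriptive rates of QTc above 480 or 500 msec, and of increases above 60 msec, under oxaliplatin-based induction. The protocol shows interest in QTc: exclusion criterion 18 names prolongation beyond 470 ms, and Section 6.5.1 asks for caution when QTc-prolonging drugs are given with oxaliplatin.

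**Working it through.** The plan states no PCSA rate or count, so there is no figure to reproduce. The check has three steps.

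**1. Is the Re-baseline ECG on-treatment in Induction?**
Inputs: last cycle starts on Day 71 (5-FU regimen, Protocol Table 2) or Day 64 (capecitabine regimen, Protocol Table 1). Capecitabine runs for two weeks, so its last dose is at about Day 77. Twelve weeks of Induction put Maintenance Day 1 at about Day 85. Re-baseline is 10 to 1 days earlier, on Days 75 to 84.

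| Last dose | Last dose + 30 | Day before Maintenance | Period ends | Re-baseline inside? |
|---|---|---|---|---|
| 5-FU/oxaliplatin, Day 71 | Day 101 | Day 84 | Day 84 | yes |
| Oxaliplatin with capecitabine, Day 64 | Day 94 | Day 84 | Day 84 | yes |
| Capecitabine, about Day 77 | Day 107 | Day 84 | Day 84 | yes |

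On schedule, the Re-baseline ECG counts as on-treatment in Induction under every regimen. A visit delayed beyond last dose + 30 days, or a missed ECG, is an exception.

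**2. What does each reading of 16.5.1 give for the Induction tables?**

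- *Scope sentence taken literally.* Only Maintenance on-treatment ECGs are used, so both Induction entries in Table 8 have no data.
- *Denominator applied by phase.* All subjects in the Safety-Maintenance set were randomised, and none has a scheduled Induction EOT visit. The denominator is 0, against up to 499 subjects with an on-treatment ECG. In the Safety-Induction set the denominator holds only those who discontinued Induction, while the numerator can also draw on the randomised subjects.
- *An EOT visit in any phase counts.* The denominator is not zero, but Induction abnormalities are divided by a count that includes Maintenance visits. The SAP does not say this is meant.

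**3. How large could the effect be in the Safety-Induction table?**
Known: 499 randomised (Protocol 8.1). Not stated: the number d with an Induction EOT visit, and the number N treated in Induction.

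*By phase.* Assume all 499 have an on-treatment Re-baseline ECG, all d have an EOT ECG, and PCSA rates are equal in the two groups. Then

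factor = (499 + d)/d

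- d = 200: 699/200 = 3.5, so a true 3% prints as 10.5%
- d = 300: 799/300 = 2.7, so 3% prints as 8.0%
- d = 400: 899/400 = 2.2, so 3% prints as 6.7%

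*Any phase.* Let f be the share of randomised subjects with a Maintenance EOT visit (assumed 0.80 to 0.95), and take N from 600 to 1000 (assumed). Then

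factor = N/[(N − 499) + 499f]

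- N = 600, f = 0.80: 600/(101 + 399.2) = 1.20
- N = 1000, f = 0.95: 1000/(501 + 474.05) = 1.03

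For the Safety-Maintenance set in Induction the factor is 1/f: 1.25 at f = 0.80 and 1.05 at f = 0.95. Over both Induction tables the range is about 1.03 to 1.25.

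**The case against.** The strongest reply is that the problem joins two provisions that conflict. Section 16.5.1 confines ECG summaries to Maintenance, and its denominator follows under that scope. Read that way, the Re-baseline ECG precedes the first Maintenance dose and is in no PCSA numerator. Protocol 8.5.5 likewise plans ECG summaries for the Maintenance Phase only, at the Discontinuation and EOT visits. This is fair, and it means that a reader should not infer that the plan is bound to publish inflated QTc rates. It does not rescue the two Induction entries in Table 8, which are then ordered with nothing to fill them.

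A reader might also infer a two- to fourfold inflation from the arithmetic above. The documents do not support that as a finding: d is not given, equal rates in completers and discontinuers are assumed, and the any-phase reading brings the factor close to 1.

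Nor should the point be carried over to the randomised comparison. In Maintenance the EOT ECG is the only scheduled on-treatment ECG, so the rule fits. EOT visits without an ECG staying in the denominator is in line with the convention in SAP Section 10, which keeps missing values in denominators and bases visit-specific percentages on subjects with some procedure at that visit. One small gap remains: an unscheduled on-treatment ECG could add a case in a subject who is still on treatment and has no EOT visit. SAP Section 10 analyses unscheduled data like scheduled data unless stated otherwise, although the ECG text speaks of notable changes and does not name the PCSA table.

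Finally, a zero denominator would show up in programming, and all ECGs are listed, so the counts are recoverable. That limits the harm but does not supply the missing rule.

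**Conclusion.** The point holds as a conflict between Table 8 and Section 16.5.1, together with a denominator that does not work for Induction. Each reading leaves the Induction PCSA tables without data, with an undefined or mismatched percentage, or divided by a count that includes another phase's visits. The zero denominator in the Safety-Maintenance/Induction table follows from the visit schedule alone, given a reading by phase. The mismatch in the Safety-Induction table also rests on Re-baseline ECGs taken on schedule. Its size is not established; the factors shown are illustrations under stated assumptions.

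Severity is minor. The Induction tables compare no randomised arms, safety is summarised descriptively, and no efficacy test, type I error or power depends on them.

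**What to change.** 1. Reconcile SAP Table 8 with 16.5.1. Either remove the two Induction PCSA entries from Table 8, or lift the Maintenance-only restriction for those tables. Either choice resolves the conflict; the first matches Protocol 8.5.5.
2. For every PCSA table kept, define the denominator as subjects with at least one on-treatment post-baseline ECG value for that parameter in that phase, and also a baseline value for criteria based on change. This follows the SAP's own laboratory convention in 16.3.1, where worst-grade summaries use only subjects with post-baseline samples. It also closes the unscheduled-ECG gap in Maintenance.
3. If the Induction tables stay, state that the Re-baseline ECG is the scheduled on-treatment ECG for subjects who complete Induction.

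The cost is a few sentences in the SAP and one change to the denominator in the table programs. No new data are needed.
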